**Study Protocol and Statistical Analysis Plan**

**Regional Anesthesia and Valproate Sodium for the Prevention of**

**Chronic Post-Amputation Pain**

**NCT01928849**

**Document date 09/25/2018**

This randomized controlled trial was conducted as part of an ongoing collaborative research initiative (Veterans Integrated Pain Evaluation Research (VIPER)) between Duke University Medical Center, Walter Reed National Military Medical Center (WRNMMC) and the Durham Veterans Affairs Medical Center (VAMC). The trial was designed to determine the extent to which the addition of oral valproic acid to regional anesthetic blockade (either peripheral nerve or epidural) and multimodal perioperative care decreases the incidence of chronic pain 3 months after amputation or amputation revision surgery. We also analyzed the trajectory of pain and functional recovery after surgery as well as epigenetic mechanisms associated with the development of chronic pain after nerve injury. Findings from the epigenetic analysis will be reported separately.

**Patient Recruitment:**

Prior to enrollment, the clinical trial was approved by the respective institutional review boards at WRNMMC, Durham VAMC, and Duke University Medical Center and the trial was registered at ClinicalTrials.gov (NCT01928849). Patients scheduled for surgical amputation or revision were screened for trial participation at the three Medical Centers from 2013 to 2017.

Among those who were screened, a significant number had been added to the surgical schedules in a non-elective fashion at the Durham VAMC and Duke University Medical Center, and were not able to be approached for consent in a non-pressured environment given the short interim period between scheduling and surgery. Similarly,

patients scheduled for amputations following trauma were often excluded because of the urgency of surgery.

Inclusion/Exclusion:

Criteria for inclusion were individuals, age 18 years and older presenting for amputation, stump revision, or surgery for mangled limb (defined as limb injury with sensory or motor deficits consistent with injury to a major nerve).

Criteria for exclusion were severe traumatic brain injury, significant cognitive deficits or dementia of any cause, substantial hearing loss without alternative means of communication, spinal cord injury with permanent deficits, current pregnancy or lactation, end-stage liver disease or hepatic encephalopathy, current therapy with valproic acid or other valproates, coumadin, chlorpromazine, olanzapine, zidovudine, or monoamine oxide inhibitors (medications affected by valproic acid metabolism), diagnosis of seizure disorder requiring anti-epileptic medication, current therapy with tricyclic antidepressants doses greater than 50mg/day, current diagnosis of malaria requiring anti-malaria medication, or allergy to valproates or valproic acid.

Randomization:

After enrollment, randomization was performed within the respective investigational drug pharmacy according to the schedule provided by our statistician. Randomization was stratified by site and surgical intervention, ie, amputation, amputation revision, or surgery for mangled limb with equal probability of assignment to the valproic acid group

or the controlled placebo group. Patients, investigators, treating medical/surgical team, and study personnel were blinded to the assignment.

At each of the study sites, following randomization, an order was placed to the Investigational Drug Service (IDS). The IDS pharmacist then assigned treatment class according to the randomization schedule previously provided by the statistician. The pharmacist then dispensed the study medication (cherry-flavored liquid or similar flavored valproic acid liquid) in single-dose containers labeled with the patient ID# and no indication of the liquid contents. At the time of surgery, the labeled study medication was transported by the research coordinator to the patient in the pre-operative area where the first dose of medication was administered by the anesthesia team. Subsequent doses were delivered to the nurse on the patient ward or intensive care unit (depending on patient disposition). The IDS retained records of study drug inventory, dispensing records, and intervention allocation. Study drug reconciliation was closely monitored for compliance in the medication administration record. The Investigational Drug Pharmacist was the only person aware of treatment allocation until the close and unblinding of the study data for analysis.

#### Intervention / Treatment

The study medication (valproic acid oral solution 250 mg per 5 mL or placebo (similar tasting flavored syrup) was then administered in single-dispense units. The initial dose was given by the perioperative anesthesia team. Subsequent doses were stored on the hospital ward or in the ICU with the patient's other medications and administered by the

nurse every 8 hours, up to 7 days or until time of patient discharge from the hospital, whichever came first. Blinding was kept intact throughout the study for all patients.

Patients in both the placebo and intervention study arms received regional anesthesia (either peripheral nerve or epidural), with multimodal perioperative management according to the standard of care at each of the three institutions. Research blood samples were collected preoperatively, postoperatively (at the end of treatment with study drug or placebo), and at clinic follow-up (3 months or at time of adjudication). Valproic acid levels were measured at the completion of drug administration to confirm study compliance.

Clinical Assessment Tools:

Clinical assessments were performed at enrollment, daily during hospitalization, and at clinic follow-up (3 months). If a patient was not available at 3 months to collect adjudication data, the study outcome was determined at the 6-month research visit. Assessment tools for pain and function included the Numeric Rating Scale (NRS), a 0-10 integer scale of pain intensity where 0/10 represents no pain and 10/10 represents the worst imaginable pain, the Brief Pain inventory, short form(BPI) (1) and the Defense and Veterans Pain Rating Scale (DVPRS) (2). Phantom and/or residual limb pain was assessed using the Groningen Questionnaire Problems Leg Amputation (GQPLA) questions (3). Neuropathic pain was measured using the Self-Reported Leeds Assessment of Neuropathic Symptoms and Signs (S-LANSS) tool (4,5). The presence of complex regional pain syndrome was determined using the Budapest Clinical Criteria

(6). Opioid and medication use was evaluated preoperatively, during hospitalization, and at the final outcome determination.

Physical Exam:

A physical exam of the surgical site was performed when possible, ie, without wound dressing). If a prosthesis was present, it was removed for the exam. If the site was not accessible at the 3-month follow-up visit, the exam was attempted again at 6 months. The exam included visual inspection for asymmetry of sweating, color, skin changes, and hair growth. Allodynia was tested with cotton wool brushing. The presence of a Tinel's sign was assessed by tapping on the most painful area and asking the patient if (s)he experienced any "sensations of pins and needles". Sensory and motor deficits were also noted.

Adjudication of Clinical Endpoint:

An adjudication committee consisting of Drs [name], [name] and [name] met for 8 sessions between March 2014 and November 2017. All 3 members were required to be present for a quorum and a majority vote determined the phenotypic endpoint. At these meetings, the post-amputation pain subtypes were adjudicated using the Duke Post-Amputation Pain Algorithm (7).

## **STATISTICAL ANALYSIS:**

Patient data were collected from patients at all study sites and entered into Research Electronic Data Capture (REDCap)TM. Data were analyzed using SAS version 9.4 (SAS Inc., Cary, NC).

Patient characteristics were summarized by treatment group using mean (SD) or median [Q1, Q3] for numeric variables and count (%) for categorical variables to assess randomization and ensure balance between treatment groups. We also compared the patient characteristics between those who did and did not return for follow-up to evaluate the possibility of response bias. Finally, plasma levels of valproic acid (VPA) were monitored to verify treatment adherence, and to determine the concentrations of VPA among treated patients.

The incidence of chronic pain, the primary endpoint, was reported by treatment arm and compared using a two-sample chi-square test and multivariable logistic regression adjusting for baseline pain severity, type of surgery (amputation, revision, other), and surgical indication (medical vs. trauma). We also investigated possible differences in treatment effect within patient sub-groups based on study site, surgery type, and reason for surgery.

Secondary endpoints and analysis of functional trajectory were planned including the change in BPI (pain and interference scores), DVPRS (pain and supplemental scores), opioid use, and neuropathic pain subtypes from baseline to time of adjudication

endpoint. Median [Q1, Q3] of the changes of mean scales from baseline was computed by arm and by assessed time between the two treatment groups via Wilcoxon rank sum test, and overall by the Wilcoxon signed rank test. Frequency and percentage of the categorical variables in above endpoints was reported overall, by treatment arm, and by assessed time. Total opioid consumption during the first and second postoperative day was summarized via median [Q1, Q3], and compared between groups via Wilcoxon rank sum test. Rates of mortalities, liver disorders, and infections was summarized by group and compared by Fisher exact or chi-square tests as appropriate to evaluate safety of valproic acid administration.

Sample size was calculated for the primary endpoint based on the assumption that 65% of the non-treatment arm patients will experience significant chronic pain (NRS  $\geq 3/10$ , averaged over previous week). We believed these estimates to be conservative, based on this group's prior research cohort (7) and prior literature demonstrating a phantom pain incidence as high as 79% in amputees from various causes Ephraim, 2005. With a 12% drop-out rate at 3 months secondary to death and loss to follow up, and a type 1 error rate of 0.05, the planned study of 224 patients would have 83% power to detect a difference in the incidence of chronic pain of 20% (45% vs 65%) between two arms using a two-sided chi-square test. Due to difficulties in enrollment the study was stopped early after 107 patients completed the primary endpoint evaluation.

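### Does the plan leave open what counts as a chronic-pain case, and who is counted, in the primary comparison?

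*Combined protocol and SAP*

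**What the plan says.** **Primary analysis (STATISTICAL ANALYSIS).** "The incidence of chronic pain, the primary endpoint, was reported by treatment arm and compared using a two-sample chi-square test". The same sentence adds a logistic regression that adjusts for baseline pain severity, surgical indication and type of surgery. Type of surgery has three levels: amputation, revision and other. The next sentence plans subgroup analyses by site, surgery type and reason for surgery.

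**Case rule (sample-size paragraph, same heading).** The calculation is said to be for the primary endpoint and assumes that "65% of the non-treatment arm patients will experience significant chronic pain". A parenthesis defines this as an NRS of at least 3/10, "averaged over previous week". The rate is supported by the group's earlier cohort and by a "phantom pain incidence as high as 79% in amputees from various causes".

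**Measurement (Clinical Assessment Tools).** The NRS is "a 0-10 integer scale of pain intensity where 0/10 represents no pain", with neither body site nor recall period. A separate sentence reads: "Phantom and/or residual limb pain was assessed using the Groningen Questionnaire Problems Leg Amputation (GQPLA) questions".

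**Adjudication (Adjudication of Clinical Endpoint).** A three-member committee met, "a majority vote determined the phenotypic endpoint", and "the post-amputation pain subtypes were adjudicated using the Duke Post-Amputation Pain Algorithm".

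**Population.** The opening paragraph states the objective for amputation or its revision. Inclusion/Exclusion also admits surgery for mangled limb, and Randomization stratifies by all three kinds of surgery.

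**The concern.** Read alone, the sentence on the primary analysis does not say what makes a patient a case. The only threshold is a parenthesis in a power calculation and names no pain site. One analyst could count a patient whose weekly average reflects back pain; another could count only pain in the operated limb. The adjudication paragraph speaks of an endpoint decided by vote, which could be taken as a second, competing route to the primary count. The objective leaves out mangled-limb surgery although such patients were enrolled, so a reader may wonder whether they are in the denominator.

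At stake is what the result describes: pain in the operated limb or pain anywhere, and in which patients. The planned 65% and 45% would carry the same doubt.

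**Working it through.** **1. The plan's own figure.** Inputs from the sample-size paragraph: 224 patients, 12% drop-out, 65% vs 45%, two-sided 0.05. Allocation is equal (Randomization).

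- Evaluable per arm: 112 × 0.88 = 98.56.
- Null standard error: √(2 × 0.55 × 0.45 / 98.56) = 0.0709.
- Alternative standard error: √((0.65 × 0.35 + 0.45 × 0.55) / 98.56) = 0.0694.
- z = (0.20 − 1.96 × 0.0709) / 0.0694 ≈ 0.88, so power is 81.1%. With unpooled variance it is 82.1%.

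The stated 83% is reproduced to within 2 points. The rates behind it are those to which the NRS parenthesis is attached.

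**2. Is the rule stated?** The sample-size paragraph has no heading of its own; it falls under STATISTICAL ANALYSIS. It names the primary endpoint and gives scale, threshold and recall window. The analysis section therefore does hold the rule, in a later paragraph than the test.

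**3. Are mangled-limb patients counted?** Set side by side:

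| Place | Kinds of surgery |
|---|---|
| Inclusion/Exclusion | amputation, stump revision, mangled limb |
| Randomization strata | amputation, revision, mangled limb |
| Covariate in the primary model | amputation, revision, other |

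Only three kinds could be enrolled, so the covariate's third level can only be mangled limb. Those patients are in the primary model, and the surgery-type subgroup analysis already separates them. The objective's shorter wording is an editorial mismatch.

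**4. How much could the pain site move the result?** Let q be the share of patients without limb pain who still reach NRS 3/10 from pain elsewhere, equal in both arms and unaffected by treatment. The documents do not give q; 0 to 0.30 is an assumed range.

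If 65% vs 45% means limb pain, the any-site rate is p + (1 − p)q and the difference is 0.20(1 − q). If it means any-site pain, the limb rate is (p − q)/(1 − q) and the difference is 0.20/(1 − q).

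| q | Any-site rates | Difference | Limb-only rates | Difference |
|---|---|---|---|---|
| 0 | 65 vs 45 | 20 | 65 vs 45 | 20 |
| 0.10 | 68.5 vs 50.5 | 18 | 61.1 vs 38.9 | 22.2 |
| 0.20 | 72 vs 56 | 16 | 56.25 vs 31.25 | 25 |
| 0.30 | 75.5 vs 61.5 | 14 | 50 vs 21.4 | 28.6 |

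In the any-site direction, power at 98.56 per arm falls from 81% to 73% at q = 0.10 and to 65% at q = 0.20. Both formulas multiply the true difference by a constant, so a true difference of zero stays zero. Under these assumptions the choice of site can dilute or sharpen an effect but cannot create one.

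**5. If the mangled-limb stratum were in doubt.** Let f be its share and e its effect in points, both assumed, with 20 points elsewhere. The pooled difference is 20(1 − f) + f·e. For e from 0 to 30 this gives 19 to 20.5 at f = 0.05, 18 to 21 at 0.10 and 16 to 22 at 0.20. At e = 20 it is 20 for every f. By step 3 this is a range for effect heterogeneity, not for doubt about inclusion.

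**6. Does the vote alter the primary count?** The committee classified subtypes, and STATISTICAL ANALYSIS lists neuropathic pain subtypes among the secondary endpoints. That gives the vote a secondary role. The randomisation text also says that only the investigational pharmacist knew the allocation until unblinding, so the committee voted blind either way.

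**The case for a change.** The case for a change is that a primary endpoint should be complete in one place: scale, threshold, window, site, time and analysis set. No sentence names the site. Clinical Assessment Tools also ties adjudication data to the determination of the study outcome when it describes the 6-month fallback, so a purely secondary role for the committee is an inference. A harder version calls this a major gap because the case rule governs the main comparison. If another rule moved the control rate to anywhere between 45% and 79% at the same relative risk (0.45/0.65 = 0.692), planned power would run from 52% to 96%.

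What stands is that the site and the committee's role are not written down, and that the objective's wording is narrower than eligibility. The harder version does not stand. Its control rates are hypothetical and no text proposes another rule. At a constant odds ratio the same control rates give only 73% to 81%. Missing outcomes and the use of 6-month values are separate questions that the site and the committee's role do not decide.

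The any-site reading is also weak. The title and objective concern pain after amputation, the physical examination is of the surgical site, and the rate is supported by an amputee cohort and a phantom-pain figure. Nothing in the plan suggests that pain elsewhere was meant to count.

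**Conclusion.** No change to the plan follows. The threshold and recall window are stated and tied to the primary endpoint, and the covariate levels place all three surgical strata in the primary model. The two details left unwritten are ones an analyst would fill sensibly from context: pain in the operated limb, and a committee that assigns subtypes.

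If the site reading were wrong, the planned 20-point difference would shift to somewhere between 14 and 28.6 points over the assumed range of q. The shift is zero if the NRS was asked about the limb only. These sizes rest on q being equal across arms and unaffected by treatment, and the documents give neither q nor the mangled-limb share. Allocation was randomised and blinded, so the comparison between arms is valid under any of these readings. The stated power is reproduced to within 2 points.

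The trial has also ended, with 107 patients evaluated. Wording added now would describe what was done and would not alter the analysis, and a separate amputation-plus-revision estimate would largely repeat the planned surgery-type subgroup work.

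### The adjusted logistic model for the primary endpoint omits site, one of the two factors used to stratify randomization

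*Combined protocol and SAP*

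**What the plan says.** Under Randomization, in the Patient Recruitment section: "Randomization was stratified by site and surgical intervention". There are three sites and three kinds of surgery.

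Under Statistical Analysis, the primary endpoint is compared between arms by a "two-sample chi-square test and multivariable logistic regression adjusting for baseline pain severity, type of surgery (amputation, revision, other), and surgical indication". The third surgery level is called other here, where the randomization text names mangled-limb surgery; I take these to be the same group. Site enters the analysis in one place only, where the plan looks at "possible differences in treatment effect within patient sub-groups based on study site, surgery type, and reason for surgery".

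Two further points bear on this. Both arms received "multimodal perioperative management according to the standard of care at each of the three institutions", so care could differ by site. The sample size, calculated for the primary endpoint, rests on detecting a difference "between two arms using a two-sided chi-square test".

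**The concern.** When randomization is stratified, the arms are balanced within strata by design. An analysis that ignores a prognostic stratification factor counts variation between strata as noise, although the design has already removed it from the comparison. The standard error is then slightly too large and the test slightly conservative. An adjusted analysis would normally carry every stratification factor. This one carries surgery type and adds two factors that were not used to stratify, but leaves out site, and no reason is given.

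What is at stake is whether the adjusted analysis matches the randomization, and a little precision if pain outcomes differ between the three institutions. Site-specific perioperative care makes such a difference plausible, but the documents report no site effect.

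**Working it through.** **1. Factors side by side**

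| Factor | Stratifies randomization | In chi-square | In logistic model | Subgroup factor |
|---|---|---|---|---|
| Site | yes | no | **no** | yes |
| Surgery type | yes | no | yes | yes |
| Surgical indication | no | no | yes | yes |
| Baseline pain | no | no | yes | no |

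**2. The plan's own power figure**

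Inputs from the sample size paragraph: 65% vs 45%, 224 patients, 12% dropout, two-sided 0.05. Evaluable per arm: n = 224 × 0.88 / 2 = 98.56.

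Power = Φ{[0.20 − 1.96·√(2 × 0.55 × 0.45 / n)] / √[(0.65 × 0.35 + 0.45 × 0.55) / n]}

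- n = 98.56: (0.20 − 1.96 × 0.0709) / 0.0694 = 0.880, power 81.1% (82.1% with unpooled variance). The stated 83% reproduces to within two points.
- n = 107 / 2 = 53.5, the number evaluated at the early stop: (0.20 − 1.96 × 0.0962) / 0.0942 = 0.122, power 54.8% (56.5% unpooled).

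These figures are for the unadjusted chi-square. Adding site to the logistic model does not change them.

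**3. Effect of adding site, by simulation**

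The design effect and N = 107 come from the documents. Everything else is assumed: three equal sites; surgery shares 60/25/15%; permuted blocks of 4 in nine strata; baseline pain with mean 5 and SD 2.5, limited to 0–10. Log-odds for none / moderate / strong effects were ±0 / 0.4 / 0.8 for site (odds ratio between extreme sites 1 / 2.2 / 5.0), ±0 / 0.2 / 0.3 for surgery, and 0 / 0.15 / 0.25 per point of baseline pain. Trauma share was either 43% at every site or 90/10/30% by site, with indication carrying from none to all of the site difference. There were 20,000 trials per setting, with Wald tests for the logistic models and an uncorrected chi-square.

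| Assumed effects | Chi-square power | Planned logistic | Plus site | Gain within setting |
|---|---|---|---|---|
| None | 55.5–56.0% | 55.1–55.7% | 55.6–56.2% | 0.5–0.6 |
| Moderate | 55.4–56.4% | 56.7–59.0% | 58.0–59.5% | 0.5–1.6 |
| Strong | 55.9–56.9% | 58.5–65.5% | 62.3–65.9% | 0.3–3.8 |

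Type I error over all settings was 4.0–5.0% for the chi-square, 4.1–5.4% for the planned logistic model and 5.2–5.7% with site added. The 3.8-point gain needs a fivefold odds difference between the extreme sites and an indication unrelated to site; type I error there moves from 4.1% to 5.2%.

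**4. Comparison at equal type I error**

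The with-site test rejects more often under the null, so nominal gains mix precision with a higher rejection rate. Three settings were rerun (20,000 trials each; planned → plus site):

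| Setting | Power | Type I error | Size-adjusted power |
|---|---|---|---|
| Moderate, same trauma share at all sites | 56.3 → 57.9% | 5.0 → 5.6% | 56.3 → 56.3% |
| Moderate, site and indication overlap | 56.8 → 57.4% | 5.5 → 5.7% | 55.0 → 55.2% |
| Strong, same trauma share at all sites | 58.9 → 63.0% | 4.4 → 5.5% | 60.9 → 61.4% |

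Size-adjusted gains are 0.0, 0.2 and 0.5 points, within simulation error. In the strong setting the nominal 63.0 − 58.9 = 4.1 points split into 60.9 − 58.9 = 2.0 from removing conservatism, 61.4 − 60.9 = 0.5 at equal size, and 63.0 − 61.4 = 1.6 from rejecting at 5.5% rather than 5%.

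A further run (8,000 trials per setting) gave nominal gains of 0.5, 1.2 and 3.6 points for none, moderate and strong effects. Type I error with site was 5.5%, 5.3% and 6.3%, and size-adjusted power did not rise. The standard error of a 5% rate is √(0.05 × 0.95 / 8,000) = 0.24 points there and 0.15 points with 20,000 trials.

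**The case against.** The best defense is that nothing is broken. Stratification already balances site, both planned tests control type I error at or close to 5%, and adding site moves the Wald test a little above 5%. The chi-square, which appears to be the deciding test, gains nothing. All of this stands, and it keeps the point small.

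The subgroup analysis by site does not fill the gap. It asks whether the treatment effect differs between sites; it does not give an overall effect adjusted for site. Nor do the documents explain why one stratification factor is in the model and the other is not.

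A reader might go further and infer that, because neither test is labelled primary, the conclusion could rest on whichever result is better. The documents do not support that as a separate defect. The sample size for the primary endpoint is built on the chi-square, the analysis text lists it first, and nothing points to the logistic model as primary. Under the assumptions above, the two planned tests disagree on significance in 3.4–15.1% of trials when the design effect is real, but taking the better of the two rejects only 5.1–6.8% under the null. A label added after the analysis could not prevent selective citation in any case, and nothing in the documents shows that any took place.

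**Conclusion.** The point holds, as a minor one. The adjusted model reflects one of the two stratification factors, and including both would match it to the randomization and avoid slight conservatism if site is prognostic.

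A reader might infer that the omission biases the comparison or costs material power. Neither is supported. Site is balanced by design. The nominal gain from adding it is 0.3 to 4.1 points across the checks, and at equal type I error it is 0.0 to 0.5. The upper end needs a site effect for which the documents give no evidence. Power of the chi-square at N = 107 is about 55% with or without the change.

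The sizes rest on assumed site shares, surgery mix, trauma shares and prognostic effects. The omission itself, and the 55%, rest on the documents alone.

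**What to change.** Add site, as a three-level class variable, to the logistic model alongside baseline pain, surgery type and indication.

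Timing decides how to report it. The adjudication committee "met for 8 sessions between March 2014 and November 2017", the pharmacist was "the only person aware of treatment allocation until the close and unblinding of the study data for analysis", the document is dated September 2018, and the analysis is described in the past tense ("Data were analyzed using SAS version 9.4"). If the data were already unblinded and analyzed, show the site-adjusted model next to the planned results as a labelled sensitivity analysis, not as a new primary analysis.

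The cost is 2 degrees of freedom on a variable already in the database. The downsides are possible overlap of site with medical or traumatic indication, which a cross-table of the two would show, and a Wald type I error of about 5.2–6.3% at N = 107.

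As a wording note only, one sentence could record that the chi-square used for sizing is the primary test and the logistic model is supportive.

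### BPI and DVPRS scores are compared by an unadjusted rank-sum test on raw change, with no between-arm estimate; a baseline-adjusted analysis would use data already collected and is often more precise

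*Combined protocol and SAP*

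**What the plan says.** The secondary endpoints in the Statistical Analysis section include "the change in BPI (pain and interference scores), DVPRS (pain and supplemental scores"). The between-arm comparison is described in one sentence: the "changes of mean scales from baseline was computed by arm and by assessed time between the two treatment groups via Wilcoxon rank sum test". The accompanying summary is descriptive: "Median [Q1, Q3] of the changes of mean scales from baseline was computed by arm". A signed rank test is added for the overall change, but that is not a between-arm comparison. For these scores the section names no covariate, no model, and no between-arm difference or confidence interval.

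Other parts of the document show that the material for an adjusted analysis exists:

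- **Primary endpoint (Statistical Analysis):** besides the chi-square test, the plan has a "multivariable logistic regression adjusting for baseline pain severity, type of surgery (amputation, revision, other), and surgical indication (medical vs. trauma").
- **Clinical Assessment Tools:** BPI and DVPRS are listed among the tools, and "Clinical assessments were performed at enrollment, daily during hospitalization, and at clinic follow-up (3 months").
- **Randomization:** "Randomization was stratified by site and surgical intervention, ie, amputation, amputation revision, or surgery for mangled limb".
- **Sample size paragraph:** "Due to difficulties in enrollment the study was stopped early after 107 patients completed the primary endpoint evaluation".

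**The concern.** Analysing raw change amounts to fixing the slope of follow-up on baseline at 1. If the true slope is lower, as it often is for pain scores measured months apart, subtracting the whole baseline value adds noise to the comparison. The plan already treats baseline pain and surgery type as worth adjusting for in the primary model, and randomization was stratified by site and surgery type. None of these enters the comparison of BPI and DVPRS.

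The second gap is in reporting. Two medians and a p-value do not tell a reader which effects on pain or interference the trial excludes. After early stopping a non-significant result is quite likely even if the drug works, so the interval is what a reader would need.

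Type I error is not at stake, and neither is the primary result.

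**Working it through.** **Plan's own figure.** The plan states no power or precision for BPI or DVPRS, so there is nothing to reproduce for these endpoints. Its 83% power is for the primary endpoint and does not bear on this point.

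**Inputs from the document.** Equal allocation; 107 patients with the primary endpoint evaluated, taken as 54 vs 53; planned evaluable number 224 × 0.88 = 197; two-sided 5% level.

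**Inputs assumed.** The baseline SD (SDb), the follow-up SD (SDf), their correlation (rho), and an effect of 0.5 × SDf. The document gives none of these, so a range is shown. It also does not state how many patients have paired scores; 107 is used in its place.

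**Step 1: variance per patient, mean change against ANCOVA.**

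- Var(change) = SDb² + SDf² − 2·rho·SDb·SDf
- Var(ANCOVA) = SDf²·(1 − rho²)
- Difference = (SDb − rho·SDf)²

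The difference is never negative, so apart from one degree of freedom ANCOVA is never less precise than the mean change. With equal SDs the ratio is (1 + rho)/2, which gives 0.65, 0.75, 0.85 and 0.90 at rho 0.3, 0.5, 0.7 and 0.8. At rho 0.5, 107 patients then give the precision of 107/0.75 = 143 analysed by mean change.

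The gain can nearly vanish. With SDb 1.5, SDf 2.5 and rho 0.5, the excess is (1.5 − 1.25)² = 0.06 on an ANCOVA variance of 6.25 × 0.75 = 4.69.

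**Step 2: interval width.** Take SDs of 2.5 and rho 0.5, with √(1/54 + 1/53) = 0.1934 and t = 1.983.

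- Mean change: SD = 2.5 × √(2 × 0.5) = 2.5; half-width 1.983 × 2.5 × 0.1934 = 0.96 points
- ANCOVA: SD = 2.5 × √0.75 = 2.165; half-width 1.983 × 2.165 × 0.1934 = 0.83 points

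**Step 3: the planned test itself.** Steps 1 and 2 concern means, while the plan tests ranks of change. The planned test was therefore simulated: 54 vs 53 patients, bivariate normal scores rounded and truncated to 0–10, baseline mean 5.0, follow-up mean 4.5, and 5,000 trials per setting (Monte Carlo SE at most 0.007). Power, rank-sum on change vs ANCOVA:

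| SDb / SDf | rho 0.3 | rho 0.5 | rho 0.7 | rho 0.8 |
|---|---|---|---|---|
| 2.5 / 2.5 | 53% vs 75% | 68% vs 82% | 87% vs 93% | 96% vs 98% |
| 1.5 / 2.5 | 68% vs 75% | 80% vs 82% | 93% vs 93% | 97% vs 98% |
| 2.5 / 2.0 | 45% vs 76% | 58% vs 82% | 78% vs 93% | 89% vs 98% |

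Rank ANCOVA gives 74, 80, 92 and 98% in the first row. In the second row it gives 73, 80, 92 and 97%, which is no gain over the rank-sum test from rho 0.5 up. With equal SDs and no effect, type I error at rho 0.3, 0.5 and 0.7 is 5.0, 4.6 and 5.2% for the rank-sum test and 5.5, 4.6 and 5.6% for ANCOVA.

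**Step 4: a strong floor.** With SDs of 2.5 and the follow-up mean lowered to 2.5, many scores pile up at 0. Power at rho 0.3, 0.5 and 0.7 (2,000 trials per setting) is 42, 54 and 72% for the rank-sum test on change, 72, 78 and 90% for ANCOVA, and 72, 78 and 91% for rank ANCOVA. Type I error stays between 4.1 and 5.6% for all three.

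**The case against.** The strongest reply is that nothing here is an error. A rank-sum test on change is valid in a randomized trial, suits bounded scores and matches the planned medians. A preference for ANCOVA could be put to almost any trial that reports change scores. The size of the gain depends on SDs and a correlation that the document does not give, and it runs from about 31 power points to about 1 or less across the table. The variance formula concerns mean change, not ranks. The simulations adjust for baseline only, so no gain from site or surgery type has been shown. Finally, the analysis appears to be done.

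Much of this stands, and it limits the claim to one of efficiency and reporting on secondary endpoints. It does not remove the point. The simulations address the rank test directly, and a floor effect, the likeliest reason to prefer ranks, widened the gap. Adjusting for the stratification factors follows from the design and does not need a demonstrated power gain. The missing between-arm interval is a gap whatever the correlation is.

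Two details deserve acceptance. Rank ANCOVA gives no difference in score units. And choosing among models after seeing results by arm would make the analysis data-dependent.

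**Conclusion.** The concern holds. The planned comparison of BPI and DVPRS uses no covariates and gives no between-arm estimate, although baseline scores, surgery type and site are all available. The planned test is valid, so the possible loss is one of precision and interpretability.

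Under equal SDs and a 0.5 SD effect, the power given up is about 22 points at rho 0.3, 14 at 0.5, 6 at 0.7 and 2 at 0.8. It is larger if scores are more variable at baseline than at follow-up, and close to nil if they are much less variable at baseline and rho is 0.5 or more. Where this trial falls cannot be read from the document. These figures also assume that all 107 evaluated patients have paired scores. The change is one that should be made, with medium confidence in how much it would gain.

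**What to change.** Analyse each follow-up BPI and DVPRS score with its own baseline value, surgery type and site as covariates. ANCOVA is the natural form; rank ANCOVA or a proportional odds model can be used if scores are skewed. Settle the choice without reference to results by arm. Report the adjusted difference with its 95% confidence interval, or the odds ratio with its interval under proportional odds. If rank ANCOVA is chosen, pair it with an estimate that has an interval, such as a Hodges-Lehmann shift, noting that this shift is not baseline-adjusted. Keep the planned medians and rank-sum test alongside, and state how many patients have paired scores.

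The cost is minor programming and no new data. The document is dated 09/25/2018, and the adjudication committee "met for 8 sessions between March 2014 and November 2017"; the Statistical Analysis section describes the analysis in the past tense. The adjusted analysis should therefore be labelled post hoc unless it was specified before unblinding.
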